9.6 Statistical Methods

9.6.1 Statistical Methods for Immunogenicity Analyses

Estimation of percent seroconversion

Within a study arm, the point estimate of percent seroconversion is calculated as the percent of participants with evaluable serology result at 1 month post last dose (Month 7) who seroconvert at 1 month post last dose (Month 7), where seroconversion is as defined in Section 9.4.1. Calculation of the corresponding 95% CI is based on the exact binomial method proposed by Clopper and Pearson (1934).

Estimation of percent seropositivity

For each of the Months 18 and 30 time points, within a study arm, the point estimate of percent seropositivity for a given HPV type is calculated as the percent of participants with evaluable serology result with cLIA titer at or above the serostatus cutoff for the given HPV type. Calculation of the corresponding 95% CI is based on the exact binomial method proposed by Clopper and Pearson (1934).

Estimation of GMTs

Within a study arm, GMTs and corresponding 95% CI will be derived by taking the antilogarithm of the mean and corresponding 95% CI (calculated based on the t-distribution) of the mean of the log-transformed anti-HPV titers. Anti-HPV titers reported as less than the LLOQ of the relevant anti-HPV type will be replaced by the half of the LLOQ in the log-transformation of anti-HPV titers.

PRODUCT: V503
PROTOCOL/AMENDMENT NO.: 066-02

Table 7 Analysis Strategy for Immunogenicity Variables

Endpoint/Variable (Description, Time Point)	Primary vs. Supportive Approach	Statistical Method	Analysis Population	Missing Data Approach	
Primary Endpoints				_	
Seroconversion to each HPV 6, 11, 16, 18, 31, 33, 45, 52 and 58 at 1	Р	Point estimate, 95% CI by exact	PPI	Observed	
month post last dose (Month 7) following 3 doses of 9vHPV vaccine	S	binomial method	ANPS	data only	
Seroconversion to each HPV 6, 11, 16, 18, 31, 33, 45, 52 and 58 at 1	P	Point estimate, 95% CI by exact	PPI	Observed	
month post last dose (Month 7) following 2 doses of 9vHPV vaccine	S	binomial method	ANPS	data only	
Secondary Endpoints	!	-1			
GMTs to each HPV 6, 11, 16, 18, 31, 33, 45, 52 and 58 at 1 month post last	P	Point estimate	PPI	Observed	
dose (Month 7) following 3 doses of 9vHPV vaccine	S	and 95% CI	ANPS	data only	
GMTs to each HPV 6, 11, 16, 18, 31, 33, 45, 52 and 58 at 1 month post last	Р	Point estimate	PPI	Observed	
dose (Month 7) following 2 doses of 9vHPV vaccine	S	and 95% CI	ANPS	data only	
Abbreviations: P = Primary, PPI = Perparticipants with serology	-protocol immuno	genicity, $S = Suppo$	rtive, $ANPS = al$	ll naïve	

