6.3 Measures to Minimize Bias: Randomization and Blinding

6.3.1 Intervention Assignment

IRT system will be used to allocate participants to either the 3-dose or 2-dose regimen arms based on gender and age at the time of providing the informed consent.

Fifteen-years-old boys will be assigned to the 3-dose regimen arm until the boys 3-dose regimen arms reaches 100 participants. Girls aged 9 to 14 years will be assigned to the 2-dose regimen arm without randomization until the girls 2-dose regimen arm reaches 100 participants.

Boys aged 9 to 14 years will be randomized in a 1:1 ratio to either 3-dose or 2-dose regimen until 100 participants are enrolled in each of the 3-dose and 2-dose regimen arms. If the combined 9- to 14-year-old boys randomized to the 3-dose regimen and the 15-year-old boys assigned to the 3-dose regimen reach 100 participants before the 9- to 14-year-old boys randomized to the 2-dose regimen reaches 100 participants, randomization of 9 to 14 year-old boys to the 3-dose regimen will be stopped, and subsequent 9- to 14-year-old boys enrolled will be allocated to the 2-dose regimen until the boys 2-dose regimen arm reaches 100 participants. Similarly, if the boys 2-dose regimen arm reaches 100 participants before the boys 3-dose regimen arm reaches 100 participants, randomization of 9- to 14-year-old boys into the 2-dose regimen arm will be stopped and subsequent 9-to 14-year-old boys enrolled will be allocated to the 3-dose regimen until the boys 3-dose regimen arm reaches 100 participants.

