8.9.3 Discontinued Participants Continuing to be Monitored in the Study

Participants who discontinue study vaccinations but continue in the study will attend study visits per the SoA (Section 1.3). However, serum will not be collected at the Month 7 study visit or subsequent visits from participants who did not complete the specified study vaccination regimen.

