9 STATISTICAL ANALYSIS PLAN

This section outlines the statistical analysis strategy and procedures for the study. Changes to analyses made after the protocol has been finalized, but prior to final database lock, will be documented in a supplemental statistical analysis plan (sSAP) and referenced in the Clinical Study Report (CSR) for the study. Post hoc exploratory analyses will be clearly identified in the CSR.

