9.2 Responsibility for Analyses/In-house Blinding

The statistical analysis of the data obtained from this study will be the responsibility of the designee/Clinical Biostatistics department of the Sponsor. This trial is being conducted as an open-label study, i.e., participants, investigators, and Sponsor personnel will be aware of participant treatment assignments after each participant is enrolled and treatment is assigned.

First database lock will be executed when all girls aged 9 to 14 years old in the 2-dose arm have either completed the Month 7 visit (1 month post last dose) or discontinued from the study before that time to report on base phase analysis for this arm.

A second database lock will be executed at end-of-study to report on base phase analysis for the 2-dose and 3-dose arms in boys and on extension phase analysis for all study arms for safety and persistence of immune response.

Summaries of the primary and secondary immunogenicity endpoints will be reported in Integrated Summary of Immunogenicity reports where in addition to reporting the immunogenicity results in this study, the study results will be compared with immunogenicity results in studies of 16 to 26 year-old Japanese males and females who received 3 doses of the 9vHPV vaccine for the purpose of immunobridging efficacy in 16 to 26 year-old Japanese males and females to 9 to 15 year-old Japanese boys and girls. The results of the 2-dose arm in girls and the 2-dose and 3-dose arms in boys will be reported in two separate integrated Summary of Immunogenicity reports. The details about the analysis will be documented in a separate iSAP.

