9.5 Analysis Populations

9.5.1 Immunogenicity Analysis Populations

Per-Protocol Immunogenicity (PPI) Population

The PPI population will serve as the primary population for the analysis of immune response to each HPV-types. To be included in this population, participants must:

- (1) Have received all required vaccinations of 9vHPV vaccine with the correct dose within acceptable day ranges (see Table 5).
- (2) Have provided blood samples for serology testing within 21 to 49 days post last dose.
- (3) Be seronegative to the appropriate HPV type(s) at Day 1.

(4) Have no other protocol violations that could interfere with the evaluation of participant's immune response to the study vaccine.

61

The final determination on protocol violations, which will be used for determining the PPI population, will be made prior to the database lock and will be documented in a separate memo.

Table 5 Acceptable Day Ranges for Vaccination Visits

	Protocol Specified	Day Range for Inclusion in Statistical Analysis				
Vaccination Dose	Visit Window	(Relative to Day 1 [†])				
	3-Dose [0,2,6 re	gimen]				
Dose 1	Day 1 [†]	0				
Dose 2	Month 2 ± 3 weeks	36 to 84				
Dose 3	Month 6 ± 4 weeks	148 to 218				
	2-Dose [0,6 regimen]					
Dose 1	Day 1 [†]	0				
Dose 2	Month 6 ± 4 weeks	148 to 218				
† Day 1 refers to the date wh	en vaccination dose 1 was administer	ed.				

Table 6 Acceptable Day Ranges for Collection of Serum Samples

Study Visit	Sample Type	Target Collection Day (Relative to Day 1)†	Day Range for Inclusion in Statistical Analysis (Relative to Day 1†)			
Day 1	Serum	0	-14 to 0			
Month 7	Serum	30 days post last dose	21 to 49 post last dose			
Month 18	Serum	548	366 to 730			
Month 30	Serum	913	731 to 1004			
† Day 1 refers to the date when vaccination dose 1 was administered. For Month 7, indicated target collection/day range						
is relative to date	is relative to date of injection of last dose of 9vHPV vaccine.					

All Naïve Participants with Serology (ANPS) Population

A supportive immunogenicity analysis will be carried out on the all type-specific naïve participants with serology population. To be included in this population, participants must:

- (1) Have received at least 1 vaccination.
- (2) Have provided serum samples with evaluable results.
- (3) Be seronegative to the appropriate HPV types at Day 1.

For each of the PPI and ANPS analysis populations:

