9.10 Subgroup Analyses

No subgroup analyses are planned for this study.

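### Should the plan estimate the 2-dose versus 3-dose contrast in the boys aged 9 to 14 it randomises?

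*Combined protocol and SAP*

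**What the plan says.** Section 6.3.1 sets the allocation: "Boys aged 9 to 14 years will be randomized in a 1:1 ratio to either 3-dose or 2-dose regimen". Fifteen-year-old boys go directly to 3 doses and girls directly to 2 doses, without randomisation. If the boys' 3-dose arm fills first, "subsequent 9- to 14-year-old boys enrolled will be allocated to the 2-dose regimen until the boys 2-dose regimen arm reaches 100 participants"; a mirror rule covers the opposite case.

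Section 9.6.1 estimates seroconversion, seropositivity and GMTs arm by arm. For titres: "Within a study arm, GMTs and corresponding 95% CI will be derived by taking the antilogarithm of the mean", with t-based limits. Section 9.10 adds: "No subgroup analyses are planned for this study".

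Three other places show that this is deliberate. Section 9.3 declares the study estimation-only, with no hypothesis tested. Section 9.6.2 gives the absence of any comparison between arms as the reason for dropping the Sponsor's usual tiered safety analysis. The objectives in Section 3 are all stated per arm, except persistence at Months 18 and 30, which is stated without any contrast.

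The only comparison described is across studies. Under Sections 4.2 and 9.2, the boys' arms are compared with Japanese males aged 16 to 26 who receive 3 doses in V503-064, under a separate integrated plan (the iSAP).

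**The concern.** Randomisation is the strongest comparative tool a trial has, and here it seems to be put in place and then left unused. Section 2.1 presents fewer doses as an alternative to the 3-dose regimen, so a reader will naturally ask how the two sit side by side in boys of the same age, tested concurrently in the same assay.

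The published arm results will not answer that cleanly. Fifteen-year-olds are only in the 3-dose arm. If the 3-dose arm fills first, the last boys in the 2-dose arm are placed there without randomisation. A casual comparison of the two boys' arms therefore mixes regimen with age and enrolment time. At stake would be a clean description of relative titres through Month 30, available from blood already being drawn.

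**Working it through.** **1. The plan's own figures.** Section 9.9 takes n = 95 evaluable per arm and true seroconversion of 99%.

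- Clopper-Pearson at 94/95 gives 94.27% to 99.97%, a half-width of 2.85 points (stated: about 3).
- A point estimate above 90% needs at least 86/95. The probability exceeds 0.9999 for one type, and for all nine if independent (stated: at least 0.99).
- A lower limit of at least 90% needs at least 92/95. The probability is 0.984 for one type and 0.984^9 ≈ 0.869 for nine independent types. The stated 0.88 is not said to refer to all nine; it is met for one type and narrowly missed for nine under independence. This has no bearing on the present point.

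All of these are single-arm quantities. Nothing was sized for a contrast between regimens.

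**2. Questions against planned answers.**

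| Question | Planned answer |
|---|---|
| Month 7 seroconversion, each arm (Section 3) | Within-arm percent, exact CI; PPI primary, ANPS supportive |
| Month 7 GMT, each arm (Section 3) | Within-arm GMT, t-based CI; same two populations |
| Persistence at Months 18 and 30 (Section 3) | Within-arm GMT and percent seropositive (Section 9.4.1) |
| Efficacy inference in boys (Section 4.2) | Comparison with males 16 to 26 in V503-064, under the iSAP |
| 2 versus 3 doses in boys 9 to 14 | Not asked |

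Every question asked has a matching analysis. The 2-dose evidence in Section 2.1 also uses adult females on 3 doses as its benchmark, not same-age 3-dose recipients.

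**3. Does age mixing damage a planned estimate?** The number of 15-year-olds is not given. Let s be their share of boys presenting (assumption). The boys needed to fill the 3-dose arm are N = 100/(s + (1 − s)/2).

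| s | N | Aged 15 | Randomised per arm | Later non-random 2-dose | Evaluable per arm at 95% |
|---|---|---|---|---|---|
| 0.05 | 190.5 | 9.5 | 90.5 | 9.5 | 86 |
| 1/7 | 175 | 25 | 75 | 25 | 71 |
| 0.25 | 160 | 40 | 60 | 40 | 57 |

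If 15-year-olds' GMT is g times that of boys 9 to 14 (assumed 0.6 to 0.8), the 3-dose GMT is multiplied by g raised to their fraction of the arm. At s = 1/7: 0.6^0.25 = 0.880 and 0.8^0.25 = 0.946, a fall of 12% to 5%. The arm's own CI factor is exp(t × SD/√95); for an assumed SD of ln titre of 0.8 to 1.4 it is 1.18 to 1.33. The shift as a factor is 1/0.880 = 1.14 to 1/0.946 = 1.06, which is smaller. Only in the extreme case (s = 0.25, g = 0.6) does it reach 1/0.6^0.40 = 1.23, above the narrowest factor but below the widest.

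In every case this is no bias against the stated target: the 3-dose objective covers boys 9 to 15, so 15-year-olds belong in it.

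**4. What the extra contrast would be.** The CI factor for a GMT ratio is exp(t × SD × √(2/n)). For SD 0.8 and 1.4:

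- n = 86: 1.27 and 1.52
- n = 71: 1.30 and 1.59
- n = 57: 1.35 and 1.68

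The difference in percent seropositive at 71 per arm has a half-width of 5.1 to 13.1 points when both arms are 100% down to 80% positive. Nine types at three time points give 27 ratios and 27 differences, or 2 × 54 = 108 estimates over PPI and ANPS.

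None would use the full randomised set, because "serum will not be collected at the Month 7 study visit or subsequent visits from participants who did not complete" the assigned regimen. Both populations therefore contain only regimen completers at Month 7, and PPI also applies a second-dose window of 36 to 84 days in the 3-dose arm only.

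**The case for a change.** The best case for the addition is that it is legitimate and cheap. A ratio with a CI is estimation, so it fits an estimation-only study and needs no test, margin or alpha. Its precision would be useful: with 71 per arm, even the wide factor of 1.59 separates a twofold difference from equality (2/1.59 = 1.26). The analysis set has to be restricted to boys randomised while both arms were open, and that rule is better fixed in advance. There is also time to do so: Section 9 allows changes to be recorded in a supplemental plan before final lock, and Section 9.2 says "A second database lock will be executed at end-of-study to report on base phase analysis for the 2-dose and 3-dose arms in boys".

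Much of this stands. The contrast is feasible, is not planned in these documents, and would interest readers. Anyone who places the two boys' arms side by side should remember the age and enrolment differences.

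It does not show a defect. The ratio has no decision, threshold or conclusion attached to it anywhere in the plan. Randomising without a planned contrast is not incoherent either: it prevents regimen choice from determining which boys aged 9 to 14 enter each arm while both are open. The restriction to completers weakens the randomised label. Because the study is open-label and the boys' lock comes at the end, a supplemental plan written late could follow sight of earlier titres. Finally, the iSAP is not among these documents, so a regimen contrast there is neither shown nor excluded.

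**Conclusion.** The point does not hold as a criticism of the plan. Leaving out the regimen contrast is a declared choice, consistent across Sections 3, 9.3, 9.6.2 and 9.10. Followed as written, the plan answers its own per-arm questions and supplies the boys' data for the bridging to adults in Section 4.2.

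No stated number, rule or conclusion would be corrected by adding the ratio. The age mix moves the 3-dose GMT by 5% to 12% at a one-in-seven share of 15-year-olds, within a CI factor of 1.18 to 1.33, and those boys are part of that arm's target population. The contrast itself would carry a CI factor of about 1.27 to 1.68 and would describe completers only.

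These sizes rest on assumed values for the share of 15-year-olds (5% to 25%), the SD of ln titre (0.8 to 1.4) and the age effect (0.6 to 0.8); only the 5% loss comes from Section 9.9. The conclusion does not depend on them: it follows from the objectives and the declared analysis. The Sponsor may add an exploratory ratio if it wishes, but nothing in the plan requires it.

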9.6.2 Statistical Methods for Safety Analyses

Safety and tolerability will be assessed by clinical review of all relevant parameters including adverse events (AEs).

The analysis of safety results usually follows a tiered approach in the studies conducted by the Sponsor. However, this study has no comparison between study arms. Thus, the following summaries will be provided as described in Table 8.

- Incidence is defined as (number of participants with the indicated endpoint divided by the total number of participants with follow-up over the relevant period)*100%.

- For the measured adverse events of redness and swelling, 0 to 1 inch will be categorized as mild intensity, >1 inch to 2 inches will be categorized as moderate intensity, and >2 inches will be categorized as severe intensity.

The specific events of interest in this study will be injection-site prompted adverse events on the VRC, such as pain/tenderness, swelling and redness/erythema occurring Day 1 through 5 following any vaccination, and elevated temperature (≥37.5°C), from Day 1 through 5 following any vaccination.

Table 8 Analysis Strategy for Safety Parameters

		Follow-Up	Period	
		After Any	Vaccination Visit	
	Within			
	study			Any Time
	arm	Day 1	Day 1	During
Adverse Event Endpoint	95%CI [∥]	to Day 5 [†]	to Day 15 [†]	Study
Clinical AEs/vaccine-related AEs				
Any AEs/vaccine-related AEs			•	
Deaths				•
Injection-site AEs/vaccine-related AEs				
Injection-site AEs/vaccine-related AEs of pain/tenderness,	•	•		
swelling, and redness/erythema	•	•		
Other injection-site AEs/vaccine-related AEs				
Severe injection-site AEs§/vaccine-related AEs	•	•		
Number (%) of participants by maximum intensity rating,		•		
over all injection-site AEs§/vaccine-related AEs				
Number (%) of participants by maximum intensity rating,		•		
within each of the categories of injection-site AEs [§] /vaccine-related				
AEs				
Systemic AEs/vaccine-related AEs	ı		_	1
Any systemic AEs/vaccine-related AEs	•		•	
Number (%) of participants by maximum intensity rating,			•	
over all systemic AEs/vaccine-related AEs				
Temperatures	ı	1	_	1
Elevated temperatures#	•	•		
Maximum temperatures ^{††}		•		
AEs of Special Interest				
Serious AEs	•		•	•
Serious vaccine-related AEs	•		•	•
New medical conditions ^{‡‡}				•
Pregnancy outcomes				•
Pregnancy outcomes				•

[†] The day of vaccination is counted as Day 1. Day 1 to Day 5 refers to the period within 4 days of a vaccination. Day 1 to Day 15 refers to the period within 14 days of a vaccination.

For the measured adverse events of redness and swelling 0 to 1 inch will be categorized as mild, >1 inch to 2 inches will be categorized as moderate and >2 inches will be categorized as severe.

[#] Defined as maximum (over the follow-up period) temperature ≥37.5°C.

^{††} Distribution of maximum temperatures over the relevant follow-up period.

^{‡‡} Including new medical conditions considered potentially of an autoimmune nature.

The exact binomial method proposed by Clopper and Pearson (1934).

AEs = Adverse events; CI = Confidence interval

9.6.3 Summaries of Baseline Characteristics, Demographics, and Other Analyses

Baseline characteristics and demographic variables

Baseline and demographic characteristics; prior and concomitant therapies; counts and percent of participants screened, enrolled, vaccinated and the primary reason for discontinuation; will be summarized in tabular format by study arm. No statistical hypothesis tests will be performed on these characteristics.

9.7 Interim Analyses

No interim analyses are planned in this study.

9.8 Multiplicity

Not applicable. The study is an estimation-only study.

9.9 Sample Size and Power Calculations

A total sample size of 300 participants will be enrolled. 100 participants will be enrolled in each study arm. When the discontinuation rate and exclusion from the HPV type-specific PPI population is at most 5%, at least 95 participants in each study arm will be evaluable for the analysis of immune response at 1 month post last dose (Month 7). In each arm, at least 95 participants evaluable per study arm will allow estimation of percent seroconversion that has a corresponding 95% CI with half-width of about 3 percentage points, assuming true percent seroconversion of 99%. In addition, at least 95 participants evaluable per study arm provides at least 0.99 probability to demonstrate that the point estimate of percent seroconversion exceeds 90% for all of 9 HPV types when the true percent seroconversion is 99%. At least 95 participants evaluable per study arm provides at least 0.88 probability to attain a lower limit of 95% CI of percent seroconversion equal to or more than 90% when the true percent seroconversion is at least 99%.

For the safety analysis, all participants are expected to be evaluable. If no SAE are observed among the 100 participants per study arm, this study will provide 95% confidence that the underlying percentage of participants with an SAE is <3.0% in each study arm.

The estimate and the half-width of the 95% confidence interval for the underlying percentage of participants with the adverse event given various hypothetical observed number of participants with an adverse event within the study arm are provided in Table 9. These calculations are based on the exact binomial method proposed by Clopper and Pearson (1934).

Table 9 Estimate of Incidence of Adverse Event and Half-width of 95% Confidence Interval Based on Hypothetical Number of Participants with Adverse Event among 100 Participants in the Study Arm

Hypothetical Number of Participants with Adverse Event	Estimate of Incidence	Half-width of 95% Confidence Interval†				
1	1%	2.7%				
2	2%	3.4%				
4	4%	4.4%				
8	8%	5.8%				
16	16%	7.6%				
32	32%	9.5%				
† Based on the exact binomial method (Clopper and Pearson, 1934).						

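### Is the stated probability of at least 0.88 that the seroconversion confidence limit reaches 90% unsupported by the design?

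*Combined protocol and SAP*

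**What the plan says.** Section 9.9 plans that "100 participants will be enrolled in each study arm". It continues: "When the discontinuation rate and exclusion from the HPV type-specific PPI population is at most 5" percent, "at least 95 participants in each study arm will be evaluable" at Month 7. Three statements about percent seroconversion follow for that evaluable number: a confidence-interval half-width of about 3 percentage points; a probability of at least 0.99 that "the point estimate of percent seroconversion exceeds 90% for all of 9 HPV types"; and the sentence at issue, under which this number "provides at least 0.88 probability to attain a lower limit of 95% CI of percent seroconversion equal to or more than 90" percent, and which applies "when the true percent seroconversion is at least 99" percent. The words about all nine types appear in the second statement and not in the third. Section 9.1 carries the same text.

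On the interval, Section 9.6.1 says: "Calculation of the corresponding 95% CI is based on the exact binomial method proposed by Clopper and Pearson (1934"). Sections 9.3 and 9.8 describe an estimation-only study with no hypothesis test and no multiplicity adjustment. The documents give no assumption about dependence between the nine types.

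**The concern.** A reader who recomputes the figure does not get 0.88. One type gives 0.98; nine independent types at 95 evaluable give 0.87. The natural suspicion is that 0.88 was meant as the nine-type joint probability, following the sentence before it, and is slightly too high.

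The form of the claim adds to this. It is written as a floor (95 or more evaluable, 0.88 or more), which implies that extra evaluable participants cannot lower the probability. With an exact interval they can: from 95 to 99 evaluable the number of non-responders allowed stays the same while the expected number rises.

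The figure is also the plan's only stated probability for the lower confidence limit of the primary immunogenicity endpoint. If it were wrong, the chance that at least one type in an arm falls short of a 90% lower limit could be about 15% and not the 12% a reader might infer.

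**Working it through.** **Inputs.** From Section 9.9: 100 enrolled per arm; at most 5% lost or excluded, so n = 95 to 100 evaluable; true seroconversion 99%, the least favourable value in the stated range; target lower limit 90%. From Section 9.6.1: two-sided 95% Clopper-Pearson interval. Dependence between types is not given, so I take the range from independence to complete dependence.

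**Step 1: non-responders allowed.** With x responders out of n, the lower limit is the 2.5% quantile of Beta(x, n − x + 1).

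- n = 95: 92/95 gives 0.9105; 91/95 gives 0.8957. Three are allowed.
- n = 96 to 99: still three. At n = 99, 96/99 gives 0.9140 and a fourth failure takes the limit just below 0.90.
- n = 100: 96/100 gives 0.9007; 95/100 gives 0.8872. Four are allowed.

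**Step 2: one type.** P₁ is the probability that a Binomial(n, 0.01) count of non-responders does not exceed the number allowed. At n = 95 the terms for 0, 1, 2 and 3 failures are about 0.385, 0.369, 0.175 and 0.055, which sum to 0.9845.

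**Step 3: nine types.** Under independence the joint probability is P₁⁹. At n = 95 this is 0.9845⁹ = 0.869. Under complete dependence it equals P₁.

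| n | Failures allowed | One type | Nine types, independent |
|---|---|---|---|
| 95 | 3 | 0.9845 | 0.8688 |
| 96 | 3 | 0.9839 | 0.8644 |
| 97 | 3 | 0.9834 | 0.8600 |
| 98 | 3 | 0.9828 | 0.8555 |
| 99 | 3 | 0.9822 | 0.8509 |
| 100 | 4 | 0.9966 | 0.9695 |

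**Step 4: compare with 0.88.**

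- One-type reading: every value exceeds 0.88, so the floor holds at every n from 95 to 100, by about 10 points or more.
- Nine-type reading under independence: short by 0.880 − 0.869 = 0.011 at n = 95 and by 0.880 − 0.851 = 0.029 at n = 99; met at n = 100.

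**Step 5: how fragile the shortfall is.**

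- *Correlation.* At n = 95 the joint value can lie anywhere from 0.869 (independence) to 0.984 (complete dependence), and 0.88 is inside that range. As an illustration, suppose some non-responders fail all nine types together and the remaining failures are independent. A pairwise correlation of about 0.14 then gives 0.88 at n = 95, and about 0.30 gives 0.88 at n = 99. These correlations are assumptions; so is zero.
- *True rate.* At 99.1% instead of 99.0%, the independent nine-type value is 0.906 at n = 95 and about 0.89 at n = 99, above 0.88 throughout.
- *Number of independent units.* Eight give 0.9845⁸ = 0.882 at n = 95. The documents do not say this was the basis, but it shows how small a difference in assumptions separates 0.87 from 0.88.

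**The case for a change.** The strongest case for a correction is that a stated minimum is either met or not. On the nine-type independent reading, which comes nearest to 0.88, it is missed at five of the six evaluable counts from 95 to 100. Rounding does not rescue it, since 0.869 rounds to 0.87. The value at 95 cannot serve as the floor for all larger counts, because the probability falls up to 99. The two readings are also far apart: the chance of falling short is under 2% for a single type but 13% to 15% for nine independent types, and the text does not say which is meant. Rewording would take one sentence in two places.

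Some of this stands. The sentence names neither its reading nor its dependence assumption, and the sawtooth of the exact interval is real. What does not stand is the step from there to an error in the design. Taken literally, the sentence speaks of one lower limit and omits the nine-type phrase used just before it; on that reading it is correct. The shortfall appears only if one adds exact independence among nine titers measured in a single test of one serum sample (Section 8.2.2), where positive dependence is the more plausible assumption, and a true rate of exactly 99% for all nine types. The evaluable number can itself differ by type, because the per-protocol population is type-specific (Section 9.5.1), so a ninth power at a common n is also an approximation.

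Nor does the plan require all nine types to reach a 90% lower limit. The 0.88 figure stands beside the half-width and the point-estimate probability, and none of the three is named as the basis for 100 per arm.

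**Conclusion.** No change to the plan is needed. The statement is true for one type (0.98 or higher at 95 to 100 evaluable). As a nine-type joint minimum it is 1 to 3 points optimistic at 95 to 99 evaluable, and only with independence between types and a true rate of exactly 99%. At 95 evaluable, the number the plan uses, the gap on that reading is 1.1 points.

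The figure is a planning statement in an estimation-only study. The report will give the observed percentages with exact intervals for each type and arm, whatever probability was quoted beforehand. No test, success rule, sample size or interpretation turns on whether it reads 0.85, 0.87 or 0.88. A reader who wants the exact values can derive them from the stated inputs plus one explicit assumption about dependence, as above. Naming that assumption in the text would make it tidier, but the study would run and be analysed in the same way.
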